7.2 SAEs

Per definition, a SAE is defined as any AE that either:

- Results in death (i.e., the AE actually causes or leads to death).
- Is life-threatening (i.e., the AE, in the view of the investigator, places the subject/patient at immediate risk of death when it occurs).
- Requires inpatient hospitalization or prolongation of existing hospitalization.
- Results in persistent or significant disability/incapacity (disability is defined as a substantial disruption of a person ability to conduct normal life functions).

- Constitutes a congenital anomaly/birth defect (in a neonate/infant born to a mother exposed to the investigational product(s)).

Definition of life-threatening: An AE is life-threatening if the subject/patient was at immediate risk of death from the event as it occurred, i.e., does not include an event that might have caused death if it had occurred in a more serious form. For instance, drug induced hepatitis that resolved without evidence of hepatic failure would not be considered life-threatening even though drug induced hepatitis can be fatal.

Definition of hospitalization: AEs requiring hospitalization should be considered serious. In general, hospitalization means that the subject/patient has been detained (usually involving an overnight stay) at the hospital or emergency ward for observation and/or treatment which would not have been appropriate at the study site. When in doubt as to whether hospitalization occurred or was necessary, the AE should be considered as serious.

Hospitalization for elective surgery or routine clinical procedures, which are not the result of an AE, do not need to be notified according to immediate reporting criteria. If anything untoward is reported during any procedure, this must be reported as an AE and either 'serious' or 'non-serious' attributed according to the usual criteria.

According to immediate reporting criteria, a hospitalization or prolongation of hospitalization in the absence of a precipitating clinical AE, do not need to be notified. Some examples include:

- Admission for treatment of a pre-existing condition not associated with the development of a new AE or with a worsening of the pre-existing condition (i.e., for work-up of persistent pretreatment lab abnormality).
- Social admission (i.e., subject/patient has no place to sleep).
- Administrative admission (i.e., for yearly physical examination).
- Protocol-specified admission during a study (i.e., for a procedure required by the study protocol).
- Optional admission not associated with a precipitating clinical AE (i.e., for elective cosmetic surgery).
- Hospitalization for observation without a medical AE.
- Pre-planned treatments or surgical procedures should be noted in the baseline documentation and/or for the individual subject/patient.
- Admission exclusively for the administration of blood products.

Definition of clinically/medically significant event: Important medical events that may not result in death, be life-threatening, or require hospitalization may be considered a SAE when, based upon appropriate medical judgment, they may jeopardize the subject/patient and may require medical

or surgical intervention to prevent one of the outcomes listed in this definition. Examples of such medical events include allergic bronchospasm requiring intensive treatment in an emergency room or at home, blood dyscrasias or convulsions that do not result in inpatient hospitalization, or the development of drug dependency or drug abuse. Clinically/medically significant events MUST be reported as SAEs.

In this clinical trial and as defined in this protocol, SAEs and hospitalizations unequivocally and solely related to established tumor progression of disease will NOT be treated as SAEs for reporting obligations.

Selected non-serious and serious AEs are also known as ECI and must be reported within 24 hours to the Sponsor.

For the time period beginning when the consent form is signed until treatment allocation first dose of study treatment, any ECI, or follow up to an ECI, that occurs to any subject must be reported within 24 hours to the Sponsor if it causes the subject to be excluded from the trial or is the result of a protocol-specified intervention.

For the time period beginning at treatment allocation first dose of study treatment through 90 days following cessation of treatment, or 30 days following cessation of treatment if the subject initiates new anticancer therapy, whichever is earlier, any ECI, or follow up to an ECI, whether or not related to Incyte, must be reported within 24 hours to the Sponsor.

7.3 Events of clinical interest (ECI) for INCMGA00012 (retifanlimab)

The table 5 shows the expected SAE.

Table 5. SAEs

MedDRA System Organ Class Preferred Term	Overall SAR Frequency n (%) Frequency Category
Gastrointestinal disorders	
Colitis	4 (0.7) Uncommon
Respiratory, thoracic and mediastinal disorders	
Pneumonitis	3 (0.5) Uncommon

Note: Frequency is expressed as the number (n) and percentage (%) of the total number of participants (N) exposed to the study drug as monotherapy who have experienced the SAR.

Please refer to the most updated INCMGA00012 (retifanlimab) IB for further detailed information related to AEs.

Overdose of INCMGA00012 (retifanlimab) product. There are no human or animal data regarding overdose of INCMGA00012 (retifanlimab). Treatment of overdose should consist of general supportive measures”.

All SAEs/ECIs that have not resolved by the EoS, or that have not resolved upon discontinuation of the subject/patient's participation in the study, must be followed until any of the following occurs:

- The event resolves.
- The event stabilizes.
- The event returns to baseline, if a baseline value/status is available.
- The event can be attributed to agents other than the investigational product or to factors unrelated to study conduct.
- It becomes unlikely that any additional information can be obtained (subject/patient or health care practitioner refusal to provide additional information, lost to follow-up after demonstration of due diligence with follow-up efforts).

7.4 AEs Reporting and Other Safety Related Issues Reporting

For serious and non-serious AEs, the reporting period to the Sponsor (or its designated representative) begins from the time that the patient provides ICF.

Reporting period for SAEs/ECIs that are NOT related with the study IMP INCMGA00012 (retifanlimab) and also all non-serious AEs is as follows:

- If patient discontinues treatment during the study, until 90 calendar days after the last administration of any of the study IMP.

All study patients will be carefully monitored for the occurrence of AEs (including SAEs and ECIs) during the above specified AE reporting period.

If the investigator becomes aware of a SAE/ECI at any time after the end of administration of study treatment and believes that it is POSSIBLY RELATED to INCMGA00012 (retifanlimab), the investigator should notify the serious adverse reaction to the Sponsor immediately irrespective of the time elapsed since last administration of the study IMP.

For all \geq grade 3 AEs with causal relationship to the investigational product, a follow-up by the Investigator may be required until the event or its sequelae resolve or stabilize at the acceptable level to the Investigator, and the Sponsor concurs with that assessment.

Clearly related signs, symptoms, and abnormal diagnostic procedure results should be grouped together and reported as a single diagnosis or syndrome whenever possible. Any additional events that fall outside this definition should also be reported separately.

All AEs must be recorded in the CRF.

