3.2.4 Follow-up after treatment discontinuation

EoS will occur 12 months after the last patient has been enrolled in the study (treatment start).

Patients discontinuing the study treatment period will enter a post-treatment follow-up period during which survival and new anti-cancer therapy information will be collected every 3 months (\pm 14 days) from the last dose of investigational product until the end of study (EoS).

During this visit, status survival and post study anti-cancer therapy evaluation will be collected (telephone contact is acceptable).

LPLV: 12 months after first study dose of the last patient or progressive disease experienced in all patients or when the trial is terminated by the Sponsor, whichever is earlier.

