exposure may represent an immunologic etiology. These AEs may occur shortly after study treatment initiation or several months after the last dose of treatment. INCMGA00012 (retifanlimab) must be withheld for certain drug-related toxicities and severe or life-threatening AEs as per **Table 1** below. Dose reduction of INCMGA00012 (retifanlimab) is not permitted.

INCMGA00012 (retifanlimab) should be permanently discontinued:

- For grade 4 toxicity except for endocrinopathies that are controlled with replacement hormones.
- If steroid dosing cannot be reduced to ≤ 10 mg prednisone or equivalent per day within 12 weeks.
- If a treatment-related toxicity does not resolve to grade 0-1 within 12 weeks after last dose of INCMGA00012 (retifanlimab).
- If any event occurs a second time at grade ≥ 3 severity (also for recurrent grade 2 pneumonitis).

Table 1. Toxicity Management Guidelines for Immune-related AEs Associated with INCMGA00012 (retifanlimab).

Immune-Related Adverse Event	Toxicity Grade or Conditions (CTCAE v5.0)	Action Taken With INCMGA00012 (retifanlimab)	AE Management With Corticosteroid and/or Other Supportive Care Therapies
Pneumonitis	Grade 1	No action.	None.
	Grade 2	Withhold until \leq Grade 1.	
 Administer systemic corticosteroids per local practice followed by taper. Evaluate participants with suspected pneumonitis with radiographic imaging and initiate corticosteroid treatment. Add prophylactic antibiotics for opportunistic infections.
	Grades 3 or 4, or recurrent Grade 2	Permanently discontinue.	
Diarrhea/colitis	Grade 1	No action.	None.
	Grades 2 or 3	Withhold until \leq Grade 1.	
 Consider prompt initiation of standard anti-diarrheal agents. Administer systemic corticosteroids per local practice followed by taper. Consider prophylactic antibiotics per local practice. Consider gastrointestinal consultation and performing endoscopy to rule out colitis.
	Grade 4 or recurrent Grade 3	Permanently discontinue.	
AST/ALT elevation and/or increased bilirubin/Hepatitis	Grade 1	No action.	None.
	Grade 2	Withhold until \leq Grade 1.	
 Administer systemic corticosteroids per local practice followed by taper. Consider monitoring liver enzymes weekly (or more frequently) until liver enzyme value returns to baseline or is stable.

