5.5 General Concomitant Medication and Additional Assistance Guidelines

Concomitant treatment and prior medication are defined as non-investigational medicinal product (IMP). Concomitant treatment includes any prescribed medication or phytotherapy between the 28 days prior to the administration of the first treatment dose and the last safety visit during treatment period. All concomitant treatments will be recorded. After this time, information will only be collected on any anti-cancer drugs taken by the patient until EoS.

Information on concomitant medication will include start date, end date, brand or generic name, route of administration, dose, and treatment indication. The following concomitant treatments are permitted during the study:

- Erythropoiesis-stimulating agents (such as Procrit[®], Aranesp[®], Epogen[®]) for the supportive treatment of anemia. Blood transfusions are permitted during the study.
- The prophylactic use of granulocyte-Colony Stimulating Factor is not allowed during the first treatment cycle but can be used for cases of neutropenia arising during treatment, in accordance with the NCCN guidelines.
- Bisphosphonates and denosumab for the prevention of skeletal events.
- Prophylactic or therapeutic anticoagulation therapy such as low-molecular weight heparin or warfarin at a stable dose level.
- Mineralcorticoids (e.g., fludrocortisone).
- Medications for the treatment of diarrhea, nausea, anorexia, or vomiting.
- Any medications deemed necessary to ensure patient safety and well-being may be administered at the discretion of the Investigator.

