2. **Demographic data and medical history:** Demographic data include age and self-reported race/ethnicity. Medical history comprises clinically significant diseases, surgical interventions, history of cancer (including prior antineoplastic treatments and procedures), history of smoking, alcoholism, drug addiction, as well as any medications (e.g., prescribed drugs, over-the-counter drugs, medicinal plants, homeopathic remedies, or food supplements) used by the patient in the 28 days prior to screening visit.
3. **Weight, Height, and Vital signs:** Weight, height (only at screening), respiratory rate, blood pressure measurements (systolic and diastolic), pulse rate, and body temperature (oral, axillary, or tympanic temperature).
4. **Concomitant medication reporting:** Relevant concomitant medication will be recorded at screening and on an ongoing basis.
5. **AE reporting:** All AEs occurring during the trial and until 90 days after treatment discontinuation visit (EoT visit) have to be recorded with grading according to the NCI–CTCAE v.5.0 criteria.
6. **Tumor assessment:** All measurable and evaluable lesions should be assessed and documented at the screening visit. Evaluation consists of clinical exam with evaluation of the penis and/or inguinal region and anatomical imaging performed during the screening period should consist of:
 - a) CT of the chest, abdomen, and pelvis or MRI of the abdomen and pelvis with a non-contrast CT scan of the chest in patients for whom CT scans with contrast are contraindicated; In the event a positron emission tomography (PET)/CT scan is used for tumor assessments, CT portion of PET/CT is usually of lower quality, and should not be used instead of dedicated diagnostic CT. If the CT scan is of high quality, with oral and IV contrast, may be used with caution. Additional information from PET may bias CT assessment.
 - b) Bone scan if a subject has a known history of bone metastases or has new bone pain during screening;
 - c) Any other imaging studies as clinically indicated by the treating physician.

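### The adverse-event windows conflict, no contact scheduled after the EoT visit carries an AE enquiry, and the SAP may leave late events out of the TEAE tables

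*Protocol*

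**What the plan says.** **End of collection.** Protocol section 7.4 ends reporting of unrelated SAEs and ECIs, and of all non-serious AEs, at 90 days: "until 90 calendar days after the last administration of any of the study IMP". It makes no exception for new therapy. The same section says: "All study patients will be carefully monitored for the occurrence of AEs (including SAEs and ECIs) during the above specified AE reporting period". It also requires the investigator, on becoming aware of an SAE or ECI thought possibly related, to notify it "irrespective of the time elapsed since last administration of the study IMP". Section 7.2 sets the ECI window at 90 days after treatment stops, "or 30 days following cessation of treatment if the subject initiates new anticancer therapy, whichever is earlier". Appendix 1 footnote 5 uses a different anchor: "All AEs occurring during the trial and until 90 days after treatment discontinuation visit (EoT visit) have to be recorded". SAP section 1.5 footnote 4 repeats that rule. The EoT visit is at 28 days ± 7 after the last dose in section 3.2.3, at 28 ± 3 in Appendix 1, and within 28 days in section 6.2.

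**Contacts.** Section 3.2.4 describes the post-treatment period as one "during which survival and new anti-cancer therapy information will be collected every 3 months", with a margin of ± 14 days, and a telephone call is acceptable. The AE row in Appendix 1 is marked at screening, at the cycles and at EoT. On medication after the last safety visit of the treatment period, section 5.5 says: "After this time, information will only be collected on any anti-cancer drugs taken by the patient until EoS".

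**Late events.** Section 5.4, on AEs of possible immunologic origin, says: "These AEs may occur shortly after study treatment initiation or several months after the last dose of treatment". Section 7.1.2 also warns of immune-related reactions after the last dose.

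**Analysis.** SAP section 5.5.4 classes any AE with onset on or after the first dose as treatment emergent. Two paragraphs later it counts non-fatal AEs only to 28 days after the final dose or to the start of new anti-cancer treatment, whichever comes first.

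**The concern.** Safety and tolerability, measured by AE incidence, is a secondary objective (sections 2.2 and 2.2.1), and the drug class is one in which the protocol expects some toxicity after treatment stops. Three things then need to agree: how long events are collected, who asks about them and when, and how long they are counted in the tables. Here they do not.

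A site that follows 7.4 closes non-serious AE collection at day 90. A site that follows the schedule of assessments closes it about four weeks later. For a patient who starts a new regimen, an unrelated ECI at day 60 is reportable under 7.4 and outside the period in 7.2. Within either window, no contact after the EoT visit is charged with asking. Whatever is collected after day 28 may or may not reach the TEAE tables, depending on which SAP sentence the programmer follows. With 18 patients, one patient more or fewer with a given event moves its incidence by 1/18 = 5.6 percentage points.

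**Working it through.** The plan gives no derived figure to reproduce. The check is date arithmetic on the stated windows, counted in days from the last dose, followed by a reading of the passages side by side.

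**End dates**

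| Source | Events covered | End |
|---|---|---|
| Protocol 7.4 | Unrelated SAEs/ECIs; all non-serious AEs | day 90 |
| Protocol 7.4 | Possibly related SAEs/ECIs | none, once the investigator is aware |
| Protocol 7.2 | ECIs, default | day 90 |
| Protocol 7.2 | ECIs, if new anticancer therapy starts | day 30 |
| Appendix 1 footnote 5; SAP 1.5 footnote 4 | All AEs | EoT visit + 90 days |

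For the last row:
- EoT at day 28: 28 + 90 = day 118.
- EoT 28 ± 3 (days 25 to 31): 115 to 121.
- EoT 28 ± 7 (days 21 to 35): 111 to 125.

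The unconditional conflict is day 90 against about day 118, a difference of 28 days. The conditional conflict concerns ECIs after new therapy: day 30 in 7.2 against day 90 in 7.4 for an unrelated event.

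**Time without a scheduled AE enquiry**
- Under 7.4: 90 − 28 = 62 days; 62/90 = 69%.
- Under footnote 5: 118 − 28 = 90 days; 90/118 = 76%.

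**First follow-up contact**
- 3 months ≈ 91 days; 91 ± 14 gives about day 77 to 105.
- It can fall up to 13 days before day 90.
- It always falls before the end of the footnote 5 window, since 105 is less than 111.

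**Schedule of assessments.** The extracted table is partly broken. The AE row has three marks, while rows that reach End of Study, such as physical examination, have four. The text agrees: sections 3.2.4 and 6.2 list only survival and anti-cancer therapy for the 3-monthly contact.

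**SAP section 5.5.4.** Take a non-fatal, non-serious AE with onset on day 60. Under the onset rule it is treatment emergent. Under the 28-day rule it is not. The summaries by system organ class and preferred term are all of TEAEs, so under the second rule the event appears in none of them. It would be counted only in the overview line for subjects with any AE. Deaths and SAEs are also limited to 28 days in that paragraph, without the cut-off at new therapy.

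**The case against.** The strongest reply is that the events of most interest are already covered. A late immune-related event that is serious or an ECI is drug-related almost by definition, and 7.4 requires such events to be notified without time limit. This stands, and it removes any claim that serious related events have a closing date under 7.4. It does not close the gap: the duty starts only when the investigator becomes aware and suspects the drug, and it does not reach non-serious AEs.

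Second, the protocol does ask for monitoring. Section 7.4 requires it for all patients, section 5.3 extends it to the follow-up period, section 3.2 names safety follow-up, and section 8.7 has investigators watch for serious toxicities throughout. The End of Study visit includes symptoms, examination and laboratory tests, and section 6.5.3 turns new abnormalities at examinations into AEs. Patients who stop without progression should continue imaging, and section 6.4.1 pairs imaging with a clinical examination. A reader might infer that late events are captured only by chance; these passages do not support that. They do leave the narrower point. None attaches an AE enquiry to a contact, the imaging visits concern only patients without progression, and Appendix 1 dates End of Study from the last patient's first dose, not from each patient's own last dose.

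Third, a reader might infer three rival end dates of 30, 90 and 118 days. That is not supported either. Section 7.2 gives 90 days by default, and its 30-day limit is conditional and covers ECIs only.

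Fourth, treatment given for an AE may be captured with the AE itself, as section 7.1 implies and as the SAE form allows. That helps once the event is known. It does not help where a steroid course would have been the clue to an unrecognised event.

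**Conclusion.** The point holds in this form: the collection windows contradict each other, a duty to monitor is stated but no contact scheduled after the EoT visit is assigned to carry it out, and the SAP has two incompatible rules for late events.

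The size is 28 days between the two unconditional end dates, and 62 of 90 days (69%) without a scheduled enquiry under 7.4, or 90 of 118 (76%) under footnote 5. These are shares of calendar time, not of events missed; an event in that span can still be reported later. The documents give no rate for events after day 28, so the number lost cannot be estimated.

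A reader might infer that a low count of late events would simply show that nobody asked. The documents do not support that as the sole explanation: under the SAP's 28-day rule, non-fatal late events would stay out of the TEAE tables however actively they were sought.

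The conclusion assumes that the AE row in Appendix 1 is read correctly from a damaged table, which the text of sections 3.2.4 and 6.2 supports. It also assumes that instructions given at site initiation, which are not in these documents, do not already settle the matter. It should be corrected, but it does not affect the primary analysis.

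**What to change.** 1. **One window.** State one end date and one anchor in protocol sections 7.2 and 7.4, Appendix 1 footnote 5 and SAP section 1.5 footnote 4. The 90 days after last dose already in 7.4 would serve. State whether new anticancer therapy shortens it, and record the start date of that therapy as a flag. Keep the open-ended duty for possibly related SAEs and ECIs.

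2. **One enquiry.** Mark AE reporting in Appendix 1 at the existing first 3-month contact, and set that contact on or after the end of the window, since it can now fall from about day 77 to 105. Ask about new or worsening AEs, hospital admissions, and steroid or immunosuppressant use. Amend section 5.5 so that medication given for an AE is recorded to the same date. If the longer footnote 5 window is chosen instead, this contact must move later.

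3. **One analysis rule.** In SAP section 5.5.4, resolve the onset rule against the 28-day rule and align the result with the collection window. Alternatively, keep 28 days for the TEAE tables and tabulate later events separately.

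The cost is amendment wording, a few questions in an existing telephone contact, and a CRF page. No new visit is needed. One call asks the patient to recall about two months, and some events will be confounded by later therapy; the flag allows those to be shown apart.
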